9.0 Identification and Recruitment of Potential Participants*

9.1 Identification of Potential Participants:

How will participants be identified? (Check all that apply)

Chart reviews

By their treating physician who will then provide the study team's contact information to the potential participant/family

By their treating physician who will obtain patient/family permission to share contact information with the study team

Self-refer in response to IRB approved advertisements or websites

Through Cerner or other CM sources (e.g. databases, billing records, pathology reports, admission logs, etc.) May involve access of records by individuals not involved in the patient's care.

List of candidates provided through the Data Report Request Form

Registry of individuals interested in research opportunities

Past participant list

Participants will roll-over from another research study: Study #

Other:

9.2 Pre-Screening prior to HIPAA Authorization

Will any of the identification methods checked above involve access to Protected Health Information (PHI) prior to obtaining HIPAA Authorization?

Yes

No

- *If yes, a "Partial Waiver of HIPAA Authorization" is required. Be sure to make this selection in the "HIPAA & Confidentiality" section below and complete [Addendum E: Waiver/Alteration of HIPAA Authorization](#)*

9.3 Recruitment of Potential Participants:

- All consecutive infants admitted during the study period at the NICUs of CMKC or KUMC who meet eligibility criteria for the study will be automatically included in the study.

10.0 Procedures

10.1 Inclusion

Eligible infants who develop clinical concern for NEC for which the neonatologist decides to obtain imaging for further evaluation as part of usual clinical care will be included into the study.

10.2 Randomization

Infants who meet inclusion criteria of NEC concern as above will be randomized to either AXR arm or AXR + BUS arm based on the calendar month the infant was born. A pre-generated randomization calendar will be posted in the NICU workroom to inform the care team which arm the infant will be randomized to, and consequently which imaging test will be ordered.

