10.7 Multiple episodes of NEC concern

Infants may also develop more than one episode of NEC concern during their admission. For such instances, study infants will remain in the same randomization arm throughout the study.

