28.0 Statistical Analysis*

28.1 We will use two-tailed McNemar's test with paired measures to analyze differences in diagnostic thinking efficacy and therapeutic efficacy from pre- and post-BUS surveys. Comparison of duration of antibiotics, bowel rest, and days to full enteral feeds will be performed using Student's t-test. Kaplan-Meier curve will be used to analyze time to full feeds between the 2 groups, censoring for death, discharge/transfer out of the hospital, or 30 days following initial NEC concern. Analyses of patient outcomes (duration of bowel rest, duration of antibiotics, time to full feeds) will follow the intention-to-treat principle, with statistical significance set at a P value of < 0.05.

28.2 We will use t-test to analyze differences in mean time of BUS image acquisition and reporting. Chi-square test will be used to compare differences in proportion of BUS studies that were performed and reported per standardized protocol. Inter-rater reliability for BUS studies will be assessed by Cohen's kappa statistics.

28.3 Sample size was calculated based on our pilot study which demonstrated a mean \pm SD of duration to full enteral feeds of 16 ± 9 days per episode of NEC concern. Using this information, we generated Table 1, which shows sample sizes for a range of possible means and standard deviations, with significance level of 0.05 and 80% power. For a 1-year study with 67 to 81 distinct episodes, for an SD of +8 days, we anticipate having sufficient sample size to detect a 5- to 6-day difference in mean duration to full feeds (highlighted in gray in Table 1).

Difference of means between groups	Expected Standard Deviation		
	± 8	± 9	± 10
4 days	126	160	198
5 days	81	102	126
6 days	56	72	88

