
The research could not practicably be carried out without the requested waiver/alteration (i.e., explain why the study could not be done if permission/assent/consent were required)
	
We initially conducted a pilot study to determine the feasibility of a RCT study design of BUS for NEC evaluation. While the RCT study design itself was feasible, we found that the process of obtaining consent was not practicable. The reasons why the proposed research could not be practicably carried out without the requested waiver are detailed below and in Fig 3:
 
(1) NEC is an emergency, making traditional parental consent at time of NEC concern impossible. Because NEC can rapidly deteriorate, infants with suspected NEC require “stat” evaluation with imaging and other laboratory tests. Families approached for research during emergency situations are often unable to give proper informed consent because of physical and emotional distress. Obtaining consent at time of NEC concern would also increase the risk of delaying evaluation. For these reasons, traditional parental informed consent at time of NEC concern is not possible for our study.
 
(2) Obtaining consent prior to NEC concern will require impractically large numbers to meet sample size demands. To overcome the emergency nature of NEC, we elected in our pilot study to seek consent from all infants who meet eligibility criteria, follow consented infants over time, and randomize only consented infants who develop concern for NEC. The problem with this approach is that only 36% (20/56) of consented infants developed NEC concern for randomization into the study. Based on these numbers, we will need to successfully consent 222 infants to achieve our target sample size of 80 infants. Although mathematically possible, it would require implausibly high approach and consent rates to successfully enroll 222 infants over the 2 years of the proposed study, making this approach of obtaining consent prior to NEC concern impracticable. This approach would also intrude on many families who would not need and may not

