	
- The electronic data will be stored on a server managed by Children's Mercy. Access to the server is restricted to only those with IRB approval for the study, and it is password protected.
 
b. All PHI collected during the study will be removed once complete research data has been collected and validated through quality assurance review. We will only maintain de-identified data for potential use in future research.
 
c. PHI will not be reused or disclosed to any person or entity other than those listed in this application, except as required by law, for authorized oversight of this research study, or as specifically approved for use in another study by an IRB.

The research cannot practically be conducted without the waiver/alteration, i.e. explain why a signature for HIPAA Authorization cannot be obtained.
	
A signature for HIPPA Authorization cannot practically be obtained because we are requesting to waive parental consent for the study. Without a corresponding HIPPA waiver, we would have to approach the families of every single patient treated in the NICU at the time of the study, which would be contrary to our request for waiver of parental consent. See Appendix B for reasons why a waiver of parental consent is requested for the study.

The research cannot practically be conducted without access to and use of the PHI, i.e. explain
	
Access to and use of PHI is needed for the study for the following reasons:

SHORT TITLE: BUS for NEC

why access to PHI is needed for this study.	
(1) The month of birth will be used to determine randomization. Other elements of date will be used to calculate duration of antibiotic treatment and days to full enteral feeds.
 
(2) Name and MRN will be used to track infant's course throughout NICU admission and access electronic medical records for data collection.

---	---

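### Arms are assigned by calendar month of birth, but the t-tests and Table 1 treat every observation as independent

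*Combined protocol and SAP*

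**What the plan says.** - **Allocation.** Under section 10.2 infants "will be randomized to either AXR arm or AXR + BUS arm based on the calendar month the infant was born", following a calendar prepared in advance. Addendum E confirms it: "The month of birth will be used to determine randomization". The plan does not say how the calendar is generated, how many months each arm gets, or whether the two sites share it.
- **Analysis.** Section 28.1: "Comparison of duration of antibiotics, bowel rest, and days to full enteral feeds will be performed using Student's t-test". A Kaplan-Meier curve for time to full feeds is added, with no named test.
- **Sample size.** Section 28.3 takes its SD in "days per episode of NEC concern" and plans "For a 1-year study with 67 to 81 distinct episodes" to detect a difference of 5 to 6 days at SD 8.
- **Unit.** Section 10.7 lets an infant have several episodes, and "study infants will remain in the same randomization arm throughout the study". The Kaplan-Meier censoring runs to death, discharge or transfer, "or 30 days following initial NEC concern", which suggests one record per infant. Addendum B gives a target of 80 infants "over the 2 years of the proposed study", where 28.3 describes one year and counts episodes.

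**The concern.** When a whole birth month goes to one arm, any difference between months in case mix, staffing or practice becomes part of the difference between arms. The t-test measures its error only from the spread between observations, so it misses that component.

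The plan gives reasons not to take independence for granted. Section 10.8 leaves the length of bowel rest and of antibiotics, two of the three outcomes, to the treating neonatologist. Addendum B says the choice of imaging depends mostly on who is on duty. Section 32 has one group of neonatologists covering both units.

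If such correlation exists, a false positive on bowel rest, antibiotics or time to full feeds is more likely than 5%, and an analysis that respects the allocation has less power than Table 1 implies. If episodes are the unit, repeat episodes in one infant add a second layer of correlation. McNemar's test, which is paired within the BUS arm, and the 28.2 comparisons do not depend on the month allocation.

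**Working it through.** **1. Reproduce Table 1.** Total N for two independent means, two-sided 5%, 80% power: N = 4 × (1.96 + 0.8416)² × SD² / d².

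| Difference | SD 8: formula / stated | SD 9: formula / stated | SD 10: formula / stated |
|---|---|---|---|
| 4 days | 125.6 / 126 | 158.9 / 160 | 196.2 / 198 |
| 5 days | 80.4 / 81 | 101.7 / 102 | 125.6 / 126 |
| 6 days | 55.8 / 56 | 70.6 / 72 | 87.2 / 88 |

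All nine cells agree to within 2, the gap being rounding. Table 1 therefore contains no design effect.

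**2. Inputs for the clustered case.** From 28.3: 81 episodes for 5 days, 67 for 6 days, SD 8. Number of birth months K: 12 (the 1-year study of 28.3), or 24 (the 2 years of Addendum B, or separate site calendars over one year). Assumptions: ICC 0 to 0.10, one episode per infant, a balanced calendar drawn at random.

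**3. Design effect.** DE = 1 + (N/K − 1) × ICC. For N = 81 and ICC 0.05:
- K = 12: 1 + (6.75 − 1) × 0.05 = 1.29, effective N = 81/1.29 = 63.
- K = 24: 1 + (3.375 − 1) × 0.05 = 1.12, effective N = 81/1.12 = 72.

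**4. Type I error of the planned t-test.** Simulation, 81 episodes placed at random in the months, 12,000 replicates:

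| Months | ICC 0 | 0.02 | 0.05 | 0.10 |
|---|---|---|---|---|
| 12 | 5.2% | 6.6% | 9.0% | 13.3% |
| 24 | 5.1% | 5.5% | 7.1% | 9.0% |

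Repeat runs agree to within 0.7 percentage points. The approximation 2 × [1 − Φ(1.96/√DE)] gives 6.3%, 8.4% and 11.8% for 12 months. It is lower mainly because it assumes equal month sizes. In the same simulations a size-weighted month-level t-test on K − 2 degrees of freedom held 4.6% to 5.3%, or 4.7% to 5.6% with the ICC estimated from the data.

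**5. Power of a month-level test.** Noncentral t on K − 2 degrees of freedom, noncentrality d / √(4 × SD² × DE / N). For 5 days, N = 81, K = 12 and ICC 0.05: 5 / √(4 × 64 × 1.288 / 81) = 2.48. The critical value on 10 df is 2.228, which gives 61%.

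| Scenario | ICC 0 | 0.05 | 0.10 | Independent t-test |
|---|---|---|---|---|
| 5 days, N = 81, 12 months | 72% | 61% | 53% | 79% |
| 5 days, N = 81, 24 months | 77% | 72% | 68% | 79% |
| 6 days, N = 67, 12 months | 79% | 70% | 63% | 86% |
| 6 days, N = 67, 24 months | 84% | 80% | 77% | 86% |

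Unequal months and an estimated ICC take off a further 1 to 4 points. With 81 episodes, the difference detectable at 80% power moves from 5.0 days (independent) to 5.5, 6.3 and 6.9 days over 12 months, or 5.2, 5.5 and 5.8 days over 24.

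**6. How the calendar is drawn matters.** For a smooth seasonal effect alone (12 months, N = 81, variance share 0.02, 0.05 and 0.10), the naive type I error is 4.6% to 5.0% if months strictly alternate, but 6.5%, 9.3% and 14.0% if they are shuffled.

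**7. Repeat episodes.** The documents give no repeat rate. As an illustration only, 1.1 to 1.5 episodes per infant with within-infant correlation 0.3 to 0.8 give DE = 1 + (1.1 − 1) × 0.3 = 1.03 up to 1 + (1.5 − 1) × 0.8 = 1.40. By the normal approximation, type I error is then 5.4% to 9.8%, and power for 5 days with 81 episodes is 79% to 66%.

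**The case against.** The strongest reply is that the harm depends on an ICC nobody has seen. Birth month is a loose cluster: concern for NEC can arise weeks after birth, infants are spread over two units, and most at the level IV site are born elsewhere. At ICC 0.01 to 0.02 the approximation in step 4 puts type I error at only 5.3% to 6.3%. This stands as a limit on size. It does not supply the missing assumption.

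On power, 28.3 promises 5 to 6 days, not 5 alone. Over 24 months the detectable differences (5.2 to 5.8 days) stay inside that range, and power for 6 days with 67 episodes is 80% or more up to ICC 0.05. That also stands. Accrual at the 28.3 rate for two years would give 134 to 162 episodes and, over 24 months at ICC 0.05, 88% to 92% power for 5 days. But Addendum B's 80 infants over two years points to about 81, and more infants per month make the type I error worse. With the 200 neonates of section 8 over 12 months at ICC 0.05, DE = 1 + (16.67 − 1) × 0.05 = 1.78 and the approximation gives 14.2%.

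The loss at ICC 0 (72% against 79%) is the price of having 10 degrees of freedom, not a flaw in a t-test that would then be valid. The within-infant part applies only if episodes are analysed. The power figures describe a month-level t-test; the mixed model proposed below was not itself simulated.

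**Conclusion.** The concern holds. That the allocation and the analysis do not match is certain; how much it matters is not. For the 1-year design with 81 episodes, the planned t-test's type I error runs from 5% at ICC 0 to about 13% at ICC 0.10. Month-level power is below 80% for both planned targets: 72% to 53% for 5 days with 81 episodes, and 79% to 63% for 6 days with 67. Over 24 months the type I error reaches 9%, and the power shortfall is small or absent for 6 days up to ICC 0.05. These figures assume SD 8, one episode per infant and a randomly drawn balanced calendar. With no correlation within months and one episode per infant, the t-test keeps its 5%. This should be settled before analysis, because it bears on all three patient outcomes of Aim 1 and the choice of method should not follow the results.

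**What to change.** **In 28.1**
1. Name the analysis unit. Either make the first episode per infant primary, or keep all episodes with an infant random effect.
2. Replace the t-tests on the three durations with a linear mixed model with a birth-month random effect and Kenward-Roger degrees of freedom. Arm, site, gestational age and birth weight are fixed effects. The covariates are already collected; adjusting for them is advisable, but clustering does not require it.
3. If the calendar was a random draw, a permutation test that re-draws it is an alternative: 12 months split 6:6 give 924 calendars. It is not available if months simply alternate, since only two calendars then exist.
4. Give the Kaplan-Meier comparison a named test with month-level inference, for example a log-rank statistic with its P value from re-drawn calendars.

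**In 10.2 and 28.3**

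State how the calendar was generated, whether the sites share it, and how many birth months are expected. Reconcile the 1-year and 2-year durations. Add a design effect over a range of ICCs and restate the power or detectable difference.

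**Cost.** This is SAP wording and a revised power statement. Birth dates are already recorded, so a valid analysis needs no new data, procedures or patients. The price is wider intervals and a less favourable power figure, including some loss at ICC 0 with 12 months. Recovering 80% power for 5 days would need more birth months or more infants, which is a separate decision.

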8.0 Local Number of Participants

	Site 1 (CMKC)	Site 2 (KUMC)	Totals
Enrollment Goal: (Neonates) Number of participants to be enrolled = the number of participants to be consented or to be screened for chart reviews.	120	80	200
Enrollment Goal: (Neonatologists) Number of participants to be enrolled = the number of participants to be consented or to be screened for chart reviews.	120	80	200

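### The arm is set by birth month and posted, so it can be known before the imaging decision that creates entry, and section 28 plans only unadjusted outcome comparisons

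*Combined protocol and SAP*

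**What the plan says.** - Allocation. Section 10.2 sets the arm by the calendar month in which the infant was born. Addendum E confirms it: "The month of birth will be used to determine randomization". Section 10.2 adds: "A pre-generated randomization calendar will be posted in the NICU workroom to inform the care team which arm the infant will be randomized to". Section 10.7 keeps the same arm for later episodes.
- Entry. Section 10.1 admits eligible infants with "clinical concern for NEC for which the neonatologist decides to obtain imaging", within usual care. Section 9.3 makes inclusion consecutive and automatic once criteria are met.
- Analysis. Section 28.1 states that comparison of antibiotic duration, bowel rest and "days to full enteral feeds will be performed using Student's t-test", with a Kaplan-Meier curve for time to full feeds. It adds: "Analyses of patient outcomes (duration of bowel rest, duration of antibiotics, time to full feeds) will follow the intention-to-treat principle". No covariate is named.
- Size. Section 28.3 plans "For a 1-year study with 67 to 81 distinct episodes" and an SD of 8 days, and gives the pilot result as 16 ± 9 days.
- Data. Section 12 collects gestational age, birth weight, age at NEC concern and clinical presentation. Section 26.1 adds blood count, CRP and blood culture. Section 28 uses none of these.

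**The concern.** The arm exists from birth and can be read off a calendar, while entry depends on a later clinical judgment. If the threshold for imaging shifts with the known arm, one arm gains infants who would not have entered under the other. Those infants would probably be milder, with shorter bowel rest, fewer antibiotic days and earlier full feeds.

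Extra mild infants in the AXR + BUS arm would look like a benefit of ultrasound. Extra mild infants in the AXR arm would hide one. Intention-to-treat does not help, because it protects the comparison only among infants already entered.

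The point concerns the between-arm patient outcomes. The McNemar analysis of survey responses and the Aim 2 measures of BUS performance are not contrasts between the arms and are not affected.

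**Working it through.** **1. Order of events.** Birth month fixes the arm (section 10.2, Addendum E). The calendar is posted (10.2). NEC concern arises and the neonatologist decides whether to image (10.1). The infant is then included automatically (9.3). Consecutive inclusion acts after the imaging decision, so it cannot prevent that decision from depending on the arm. For a repeat episode the arm has already been applied (10.7).

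**2. The plan's own figure.** For equal groups, total N = 4 × [SD × (1.960 + 0.842) / d]². With SD 8 and d = 5 this gives 80.4, against 81 in Table 1. With SD 8 and d = 6 it gives 55.8, against 56. The other cells agree to the same degree. The sample-size table stands and is not in dispute.

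**3. Illustration of size.** The documents give neither input below, so both are assumed: q, the share of one arm made up of extra infants, and m, the days sooner that they reach full feeds. The true effect is set to zero, the arms are equal (n = 81/2 = 40.5), SD is 8, and episodes are treated as independent.

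- False difference b = q × m
- SD in the arm with extras = √[64 + q(1 − q)m²]
- SE = √[(64 + that SD²) / 40.5]
- Rejection rate = Φ(b/SE − 1.96) + Φ(−b/SE − 1.96)

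Low corner (q = 0.1, m = 4): b = 0.4; SD = √65.44 = 8.09; SE = 1.788; b/SE = 0.224; rate = 0.056.

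High corner (q = 0.3, m = 8): b = 2.4; SD = √77.44 = 8.80; SE = 1.869; b/SE = 1.284; rate = 0.250.

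| q | m = 4: b (days), rate | m = 8: b (days), rate |
|---|---|---|
| 10% | 0.4, 5.6% | 0.8, 7.2% |
| 20% | 0.8, 7.3% | 1.6, 13.9% |
| 30% | 1.2, 10.2% | 2.4, 25.0% |

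The false difference is 8% to 48% of the 5-day target (0.4/5 to 2.4/5). With 67 episodes and the pilot SD of 9, the rate runs from 5.4% to 18%.

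**4. The opposite direction.** If the extra infants are in the AXR arm, power for a true 5-day BUS benefit is about Φ((5 − b)/SE − 1.96). With no selection, SE = 8 × √(2/40.5) = 1.778 and power is 0.80. At b = 0.4 it is Φ(4.6/1.788 − 1.96) = 0.73. At b = 2.4 it is Φ(2.6/1.869 − 1.96), or about 0.28.

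**5. How much an entry comparison could show.** Addendum B reports that 36% of consented pilot infants developed NEC concern, and says "we will need to successfully consent 222 infants to achieve our target sample size of 80 infants". Take 222 eligible infants, 111 per arm, and a 36% entry rate. The 95% half-width for the difference in entry rates is 1.96 × √(2 × 0.36 × 0.64 / 111) = 0.126, about 13 points. That treats infants as individually allocated. Allocation is by birth month, so 13 points is optimistic and the true interval would be wider.

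**The case against.** The strongest case is that knowing the arm changes little at the moment of decision. Entry is for imaging in usual care (10.1). Both arms receive AXR (10.3), and an AXR infant can still have BUS (10.5). Addendum B says BUS is done for clinical indication and not for research alone, and describes evaluation as urgent. Waived permission removes selection at consent. The eligibility criteria are not in the text available for review, so any objective trigger for NEC concern cannot be judged. All of this stands. It weakens the motive for arm-dependent entry, but the decision is still made with the arm knowable.

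Four stronger readings are tempting, and the documents do not support them:

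- *The trial will be biased, or allocation is not random.* The calendar may itself have been randomly generated. What is shown is lack of concealment before entry.
- *The report will hold no entry numbers by arm.* The t-tests need the number analysed in each arm. Only the denominator, eligible infants who did not enter, is unspecified, and silence in a short analysis section is not a plan to omit it.
- *25% is an estimate.* It is one corner of a grid of assumed inputs. An 8-day gap is half the pilot mean of 16 days.
- *An entry comparison would settle the matter.* Step 5 shows that it is weak.

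It is also fair to object that adjusting for gestational age and birth weight may miss severity at presentation, the feature on which selection would act. That stands, and the fix adds a sensitivity analysis for it.

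**Conclusion.** The point holds as a limited one. The arm can be known before the decision that creates entry, and section 28 neither adjusts the patient-outcome comparisons nor specifies the information needed to judge whether entry differed by arm. The safeguards narrow the route without closing it.

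Size and direction are unknown. The range of 0.4 to 2.4 days, with a false-positive rate of about 5.6% to 25%, rests wholly on the assumed share and mildness of extra infants and on independent episodes. At the low end the effect is negligible. The change is worth making because the adjusted analysis uses data already planned for collection and is a reasonable choice whether or not selection occurs.

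**What to change.** Amend section 28 before outcome data are examined, keeping birth-month allocation.

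1. **Main change.** Replace the unadjusted t-tests for bowel rest, antibiotic days and days to full feeds with linear regression on arm, site, gestational age and birth weight. Add a sensitivity analysis that also includes age, recorded presentation and laboratory severity at NEC concern. Label the Kaplan-Meier curves as unadjusted.
2. **Supporting report.** Give eligible and entered infants by birth-month arm and site, with a 95% CI for the between-arm difference that allows for birth-month clustering. Tabulate characteristics at entry by arm. Define the eligible pool: section 8 describes its goal of 200 as "the number of participants to be consented or to be screened for chart reviews", and 200 × 0.36 = 72 falls within the planned 67 to 81 episodes, so 200 can be read as the screened pool.
3. **Stated limits.** Say that adjustment corrects selection only in part, and that a non-significant difference in entry does not rule selection out.

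Item 1 costs only drafting, since site is known and the other variables are already collected. Item 2 needs one new quantity, an aggregate count of eligible infants who did not enter at each site. The sponsor should first confirm that the HIPAA waiver covers it.

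Concealed individual allocation, with the arm revealed after the imaging decision is recorded, would address the cause. It adds a step before urgent imaging, and Addendum B reports that 4 of 20 pilot infants with NEC concern missed randomization. That is a trade-off for the sponsor to weigh and is not part of this fix.
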